#### Change From Baseline:

Change from baseline is the arithmetic difference between post-baseline and baseline.

#### **Duration of Treatment:**

Date of last administration of investigational product – Study Day 1 + 1

Protocol Number: 20200392

Date: 10 May 2024 Page 17 of 33

#### **DLT Observation Period:**

The DLT observation period is defined as day 1 through day 28 after the administration of the first dose of AMG 176.

#### Fridericia-corrected QT Interval (QTcF):

The Fridericia correction will be calculated from the investigator reported QT (msec) and RR interval (msec): QTcF=QT/(RR/1000)1/3.

#### Investigational Product (IP):

IP is used in reference to AMG 176.

#### Last known alive date:

Last known alive date is described in Appendix C.

#### Study Day:

Post study day 1: study day = (date – date of Study Day 1) + 1

Pre study day 1: study day = (date – date of Study Day 1)

#### Study Day 1:

Study day 1 is defined as the first day of administration of the investigational product after enrollment. The day prior to Study Day 1 is considered Day -1.

#### **Transfusion independence:**

Transfusion independence is defined as no transfusion for at least 8 consecutive weeks (56 days).

#### Treatment-Emergent Adverse Event (TEAE):

A treatment-emergent adverse event is any adverse event starting on or after the first dose of investigational product, as determined by "Did event start before first dose of investigational product" equal to "No" or missing on the Events eCRF, and up to and including 30 days after the last dose of investigational product excluding events reported after end of study date.

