^p Cytomorphology: bone marrow smears (slides) at screening, pre-dose on day 1 of cycle 2 and cycle 3 and thereafter prior to every other cycle or when clinically indicated until disease progression. Bone marrow biopsies/aspirates may be performed with a ± 3 day window.

- ^q EOT and SFU: In any case of premature treatment discontinuation, the investigator should make every effort to perform all examinations scheduled for the EOT and SFU visits. These data should be recorded, as they comprise an essential evaluation that should be performed prior to removing any subject from treatment and to allow for the evaluation of the study endpoints. The EOT visit will occur upon the decision to end the treatment (eg, due to intolerable AE, disease progression). The SFU visit will occur 30 days (+ 3 days) after last dose of protocol required therapies.
- Note: If a subject withdraws consent, it is important to distinguish between withdrawal of consent from treatment (partial withdrawal of consent) which will allow for continued follow-up in LTFU (eg, for survival) or withdrawal of consent from study (full consent withdrawal). These discussions should be thoroughly documented in the subject's medical records.
- LTFU/EOS: Long-term follow-up (LTFU) visits will occur every 3 months for up to 1 year after EOT. The EOS for a subject will occur when the subject completes the LTFU or dies, whichever occurs first.
- Note: If a subject withdraws consent, it is important to distinguish between withdrawal of consent from treatment which will allow for continued follow-up in LTFU (eg, for survival) or withdrawal of consent from study. These discussions should be thoroughly documented in the subject's medical records.
- ^s During the Long-term follow-up phase, serious adverse event(s) suspected to be related to Investigational Product will be reported to Amgen. After end of study serious adverse event(s) suspected to be related to Investigational Product will be reported to Amgen. Please refer to Section 8.4.6.1.3 for additional details.

Protocol Number: 20200392

Date: 28 April 2022 Page 28 of 149

2. Introduction

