4.4 End of Study

An individual subject is considered to have completed the study if he/she has completed the last visit or the last scheduled procedure shown in the Schedule of Activities. The total study duration for an individual subject is 7.5 months from screening through the safety follow-up visit.

The end of study (EOS) date is defined as the date when the last subject across all sites is assessed or receives an intervention for evaluation in the study (ie, last subject last visit), including any additional parts in the study (eg, long-term follow-up, additional antibody testing), as applicable.

5. Study Population

Investigators will be expected to maintain a screening log of all potential study candidates that includes limited information about the potential candidate (eg, date of screening).

Eligibility criteria will be evaluated during screening.

Before any study-specific activities/procedures, the appropriate written informed consent must be obtained (see Section 11.3).

Prospective approval of protocol deviations to recruitment and enrollment criteria, also known as protocol waivers or exemptions will not be provided.

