8.4.6.1.2 Serious Adverse Events

The investigator is responsible for ensuring that all serious adverse events observed by the investigator or reported by the subject that occur after signing of the informed consent through the safety follow-up visit or 30 days after last day of dosing interval of investigational product(s)/protocol-required therapies, whichever is later, are reported using the Events CRF.

All serious adverse events will be collected, recorded, and reported to the sponsor or designee within 24 hours of the investigator's awareness of the event, as indicated in Section 11.4. The investigator will submit any updated serious adverse event data to the sponsor within 24 hours of it being available.

Protocol Number: 20200392

Date: 28 April 2022 Page 82 of 149

Since the criteria of the CTCAE grading scale differs from the regulatory criteria for serious adverse events, if adverse events correspond to grade 4 CTCAE toxicity grading scale criteria (eg, laboratory abnormality reported as grade 4 without manifestation of life-threatening status), it will be left to the investigator's judgment to also report these abnormalities as serious adverse events. For any adverse event that applies to this situation, comprehensive documentation of the event's severity must be recorded in the subject medical records.

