#### Treatment-related Treatment-emergent Adverse Event (TRAE):

A TRAE is any TEAE whose causal relationship is marked as "Related" on the eCRF.

Protocol Number: 20200392

Date: 10 May 2024 Page 18 of 33

Event with missing relationship will be assumed to be treatment-related.

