#### 9.6.2 Adverse Events

The Medical Dictionary for Regulatory Activities (MedDRA) version 26.1 or later will be used to code all events categorized as adverse events to a system organ class and a preferred term.

Subject listing of all treatment-emergent adverse events, serious adverse events, adverse events leading to discontinuation of investigational product, treatment related adverse events, DLTs and fatal adverse events will be provided.

Subject listing of Troponin increased adverse events serious adverse events, adverse events leading to discontinuation of investigational product, treatment related adverse events, and fatal adverse events will be provided.

The grading of adverse events will be based on the guidelines provided in the Common Terminology Criteria for Adverse Events (CTCAE) version 5.0.

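### The TEAE definition drops events by report date, so an on-treatment event reported late can be missing from the treatment-emergent and treatment-related listings

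*SAP*

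**What the plan says.** The TEAE definition in SAP Section 5 has two parts. The first is an onset window: the event starts on or after first dose of AMG 176, "up to and including 30 days after the last dose of investigational product". The second is an exclusion: "excluding events reported after end of study date". The next definition builds on it: "A TRAE is any TEAE whose causal relationship is marked as" related. It adds a default for missing causality: "Event with missing relationship will be assumed to be treatment-related".

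The SAP does not define the end of study date. The protocol uses the term in two ways:
- **Study level.** Protocol Section 4.4: "The end of study (EOS) date is defined as the date when the last subject across all sites is assessed".
- **Subject level.** Protocol Section 1.3, LTFU/EOS footnote: "The EOS for a subject will occur when the subject completes the LTFU or dies, whichever occurs first". Section 8.1.6 describes a subject's completion of the study in the same way.

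On reporting, Protocol Section 8.4.6.1.2 says: "All serious adverse events will be collected, recorded, and reported to the sponsor or designee within 24 hours" of the investigator becoming aware. Section 8.4.6.1.3 still requires suspected-related serious events to be reported when the investigator learns of them after the study has ended.

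On output, SAP Section 9.6.2 plans: "Subject listing of all treatment-emergent adverse events, serious adverse events, adverse events leading to discontinuation of investigational product", followed by treatment-related events, DLTs and fatal events.

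**The concern.** The onset window already limits a TEAE to the period when AMG 176 could plausibly be responsible. The added clause does not tighten that window. It removes events that began inside it if the report came late, so classification depends on the speed of reporting and not on when the event happened.

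Treatment-emergent and treatment-related events are named components of the Part 1A primary safety endpoint. SAP Sections 9.6.1 and 10 replace the summary tables for that endpoint with subject listings, because the study closed early with few subjects. The TEAE and treatment-related listings are therefore the whole analysis of those two components, and in a small study one missing row matters.

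**Working it through.** The plan states no figure on this point, so there is none to reproduce. The check is of date logic.

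**Step 1: is there a fallback?** Protocol Section 11.4 leaves the TEAE definition to the SAP, so no protocol text overrides the clause. The missing-causality default does not help either. It sits inside the definition of a treatment-related event, which an event must first be a TEAE to meet.

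**Step 2: write out the rule.**
- As written: TEAE if first dose ≤ onset ≤ last dose + 30 days, and report date ≤ end of study date.
- Keyed to onset: the same window, and onset ≤ end of study date.

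**Step 3: apply both rules to assumed cases.** The study days are illustrative and are not in the documents. First dose is day 1 and last dose day 22, so the window closes on day 22 + 30 = 52. Each event starts on day 25 and so lies inside it. Study-level end of study is set at day 400. For a survivor, subject-level end of study is taken as one year after treatment ends: 22 + 365 = 387.

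| Event | Report day | End of study date used | As written | Keyed to onset |
|---|---|---|---|---|
| Fatal, death on day 25 | 26 | Subject, day 25 | 26 > 25: not a TEAE | TEAE |
| Fatal, death on day 25 | 26 | Study, day 400 | TEAE | TEAE |
| Non-fatal serious event | 395 | Subject, day 387 | 395 > 387: not a TEAE | TEAE |
| Non-fatal serious event | 395 | Study, day 400 | TEAE | TEAE |
| Non-fatal serious event | 410 | Study, day 400 | 410 > 400: not a TEAE | TEAE |

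The day-26 report meets the 24-hour rule if awareness was on day 25, so full compliance with the protocol does not protect the event on the subject-level reading. The last row shows that the study-level reading does not remove the problem either; it confines it to reports after last subject last visit. Every row that fails the TEAE test also fails the treatment-related test. Keying to onset classifies all the cases as TEAEs under both meanings of the date.

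**Step 4: where would an excluded event still be seen?** SAP Section 9.6.2 names serious events, fatal events and DLTs as separate items and states no treatment-emergent restriction on them. The event could therefore appear in one of those listings and be absent from the TEAE and treatment-related ones.

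**The case against.** The best counter-argument is that the term is defined, and at study level. Protocol Section 4.4 gives the definition, Section 9.4 ties the final analysis to it, and Section 8.4.6.1.3 uses end of study for the time after the study has ended. On that reading a death reported a day or a month later, while the study is running, stays a TEAE. This largely stands. A reader might infer that a subject's death sets its own cut-off, so that fatal events are systematically removed. The documents do not establish that. They only leave it open, through the Section 1.3 footnote and the reference in SAP Appendix C to an end-of-study form whose status can be dead.

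Three further points bear on size:
- A reader might infer that a treatment-related death would cease to count as a DLT. It would not. DLTs have their own criteria (Protocol Table 6-2), observation period and listing, and none of these depends on TEAE status.
- A reader might try to size the problem from the short survival after HMA failure quoted in Protocol Section 2.2.1. That would give the chance of dying inside the window, not the chance of losing TEAE status. The latter also needs the subject-level reading and the share of deaths reported on a later calendar day, and the documents give no such share.
- Report date is not among the mandatory event attributes in Protocol Section 11.4 or the Events-form dates in SAP Appendix C. Programmers may therefore apply the clause to onset, which would do no harm in these cases. It may also have been meant as a boundary between the clinical database and later reports to the safety database. Both are plausible, but neither is what the clause says, and a definition that is safe only when not followed literally should be corrected.

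**Conclusion.** The clause is wrong as written, with limited consequences. An event with on-treatment onset can lose both its treatment-emergent and its treatment-related label solely because of when it was reported.

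The extent depends on a date that the SAP leaves undefined. At study level, the loss is confined to events first reported after last subject last visit. At subject level, it also takes in a fatal event reported the day after death and a late report on a subject who has completed follow-up.

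The effect is incomplete TEAE and treatment-related listings that may disagree with the serious, fatal and DLT listings about the same event. The event does not vanish from the report, provided those other listings are run without a treatment-emergent filter, as the text reads. No frequency can be derived from the documents. Severity is minor to moderate.

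**What to change.** In SAP Section 5, either delete the exclusion, since the 30-day onset window already limits the period, or replace it with one that excludes events with onset after the subject's end of study date. If the replacement is used, say that the date is the subject's own.

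Add one sentence: subject to that onset bound where it is kept, an event with onset from first dose to 30 days after last dose that is known by database lock is a TEAE whatever its report date. This should expressly include serious events received on the paper contingency form after the electronic system closes.

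The treatment-related definition then needs no change. The cost is one clause in the SAP plus the usual reconciliation of serious events before lock.

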#### Treatment-related Treatment-emergent Adverse Event (TRAE):

A TRAE is any TEAE whose causal relationship is marked as "Related" on the eCRF.

Protocol Number: 20200392

Date: 10 May 2024 Page 18 of 33

Event with missing relationship will be assumed to be treatment-related.

#### 6. Analysis Sets

#### 6.1 Full Analysis Set

The FAS is defined as all subjects who are enrolled and receive at least 1 dose of AMG 176.

#### 6.2 DLT Evaluable Analysis Set

Subjects are considered DLT-evaluable if they experience a DLT during the DLT evaluation period, or if they complete the DLT evaluation period and receive at least 75% of the planned doses of AMG 176 and 100% of the planned dose of azacitidine.

#### 6.3 Pharmacokinetic/Pharmacodynamic Analyses Set(s)

The PK Analysis Set defined as all subjects who have received at least 1 dose of the investigational product and have at least 1 PK sample collected. These subjects will be evaluated for PK analysis unless the number of data points required for analysis is not enough, or significant protocol deviations have affected the data, or if key dosing or sampling information is missing.

#### 7. Planned Analyses

#### 7.1 Interim Analysis and Early Stopping Guidelines

As the decision was made to terminate the study early, no formal interim analysis will be performed for this study.

#### 7.2 Primary Analysis

No formal primary analysis will be performed due to early close out of the study.

#### 7.3 Final Analysis

A final analysis is planned after all available subjects have had the opportunity to complete the last study visit.

#### 8. Data Screening and Acceptance

#### 8.1 General Principles

The objective of the data screening is to assess the quantity, quality, and statistical characteristics of the data relative to the requirements of the planned analyses.

Protocol Number: 20200392

Date: 10 May 2024 Page 19 of 33

#### 8.2 Data Handling and Electronic Transfer of Data

The Amgen Global Study Operations-Data Management (GSO-DM) department will receive and store all data to be used in the planned analyses. This study will use the RAVE database.

#### 8.3 Handling of Missing and Incomplete Data

The following imputation for missing or incomplete data will be performed if required: Incomplete adverse event and concomitant medication dates missing data will be imputed as described in Appendix D.

Non-pharmacokinetic measurements ( ) that are above or below the quantification limits will be considered equal to the upper or lower limit of quantification for all analyses unless specified otherwise.

#### 8.4 Detection of Bias

Lack of protocol compliance and the potential for biased statistical analyses will be examined by assessing the incidence of important protocol deviations in each cohort.

The clinical study team will identify and document the criteria for important protocol deviations.

#### 8.5 Outliers

Outlier data will not be excluded unless scientifically justified.

PK concentration data will be evaluated for outliers by visual inspection and decisions to re-assay individual samples will be made in accordance with standard Pharmacokinetics and Drug Metabolism (PKDM) practices.

#### 8.6 Distributional Characteristics

Where appropriate, the assumptions underlying the proposed statistical methodologies will be assessed. If required data transformations or alternative non-parametric methods of analyses will be utilized.

#### 8.7 Validation of Statistical Analyses

Datasets, tables, figures, and listings will be produced and validated in accordance with SOP-430399. Standard macros will be used when available.

Protocol Number: 20200392

Date: 10 May 2024 Page 20 of 33

The production environment for statistical analyses consists of Amgen-supported versions of statistical analysis software; for example, the SAS System version 9.2 or later.

#### 9. Statistical Methods of Analysis

#### 9.1 General Considerations

Descriptive statistics on required continuous data like Troponin I and Troponin T will include means, medians, standard deviations, first and third quartiles and ranges.

When data are summarized by time, the values recorded against the scheduled time points listed in the protocol will be used. When assessing minimum/maximum increases or decreases over the study, all assessments, including unscheduled assessments will be used.

No formal statistical analysis will be performed for the study and listings will be provided.

#### 9.2 Subject Accountability

No summary of subject accountability will be required to provided.

#### 9.3 Important Protocol Deviations

Important Protocol Deviations (IPDs) categories are defined by the study team before the first subject's initial visit and updated during the IPD reviews throughout the study prior to database lock. These definitions of IPD categories, subcategory codes, and descriptions will be used during the course of the study. Eligibility deviations are defined in the protocol.

No listing of IPDs and eligibility deviations will be provided

#### 9.4 Demographic and Baseline Characteristics

Demographic and baseline characteristic will be listed.

Protocol Number: 20200392

Date: 10 May 2024 Page 21 of 33

#### 9.5 Efficacy Analyses

#### 9.5.1 Analyses of Primary Efficacy Endpoint(s)/Estimand(s)

No formal statistical analyses will be performed for primary efficacy endpoints due to early termination of the study which resulted in insufficient number of subjects.

## 9.5.2 Analyses of Secondary Efficacy Endpoint(s)/Estimand(s) The listing of responder/non-responder will be provided for Part 1A- QW Monotherapy (Dose Exploration) subjects.

#### 9.5.3 Analyses of Exploratory Efficacy Endpoint(s)

NA

#### 9.6 Safety Analyses

#### 9.6.1 Analyses of Primary Safety Endpoint(s)

No summary analysis tables will be provided for the safety endpoints. More details are mentioned in sections from 9.6.2 to 9.6.10

#### 9.6.2 Adverse Events

The Medical Dictionary for Regulatory Activities (MedDRA) version 26.1 or later will be used to code all events categorized as adverse events to a system organ class and a preferred term.

Subject listing of all treatment-emergent adverse events, serious adverse events, adverse events leading to discontinuation of investigational product, treatment related adverse events, DLTs and fatal adverse events will be provided.

Subject listing of Troponin increased adverse events serious adverse events, adverse events leading to discontinuation of investigational product, treatment related adverse events, and fatal adverse events will be provided.

The grading of adverse events will be based on the guidelines provided in the Common Terminology Criteria for Adverse Events (CTCAE) version 5.0.

#### 9.6.3 Laboratory Test Results

The subject listing of clinical laboratory will be provided for the full analysis set. The analyses of safety laboratory data for Troponin will be included as summary statistics over time by dose level

Protocol Number: 20200392

Date: 10 May 2024 Page 22 of 33

#### 9.6.4 Vital Signs

The listing of vital signs including systolic/diastolic blood pressure, heart rate, respiratory rate and temperature will be provided.

#### 9.6.5 Physical Measurements

The subject listing will be provided which will include parameters of physical measurements.

#### 9.6.6 Electrocardiogram

The listing of all on-study ECG data will be provided.

#### 9.6.7 Antibody Formation

No summary tables or listing will be provided.

#### 9.6.8 Exposure to Investigational Product

The subject listings will be provided with IP start and end date. The listing will also include planned dose, actual dose and reason for change or withheld of the planned dose.

### 9.6.9 Exposure to Non-investigational Product(s)/Auxiliary Medicinal Product(s)

NA

#### 9.6.10 Exposure to Concomitant Medication

No summary tables and listings will be provided.

#### 9.7 Other Analyses

#### 9.7.1.1.1 Pharmacokinetic Analyses

The analysis of pharmacokinetic endpoints will include data from all subjects who have received at least 1 dose of the investigational product and have at least 1 pharmacokinetic sample collected.

PK parameters for AMG 176 including, but not limited to, maximum observed concentration (Cmax), area under the concentration-time curve (AUC) and half-life (t1/2) will be estimated, if feasible.

